9.5.2 Best Corrected Visual Acuity (BCVA)

The number and percent of subjects reporting with BCVA of 20/20 or better, 20/25 or better, 20/32 or better, 20/40 or better, worse than 20/40 to 20/80, worse than 20/80 to 20/200, and worse than 20/200 at each visit will be summarized for the two study groups separately. The number and percent of subjects reporting BCVA of increase ≥ 2 lines (10 letters), increase 2 lines, increase ≥ 1 line to < 2 lines, within 1 line change, decrease ≥ 1 line to < 2 lines, decrease 2 lines, and decrease ≥ 2 lines at each postoperative visit will be calculated for the two study groups separately.

9.5.3 Other Safety Analyses

The number and percent of subjects reported with each kind of slit lamp findings, gonioscopy findings, dilated fundus examination findings, and pachymetry at each visit will be provided for the two study groups separately.

The descriptive statistics for the continuous variables will be derived for the visual field mean deviation (MD) and pattern standard deviation (PSD), and pachymetry.

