10.0 ADVERSE EVENTS

Adverse Events are defined below. Adverse events that occur in the study eye during the trial as well as other non-ocular events whether they are considered to be device related or not must be documented in the subject's records. Date of the event, its severity, treatment (if any) and the assessed relationship of the event to the study device will be recorded on the Adverse Event Form. Conditions which exist at the time the subject is enrolled do not need to be recorded on the Adverse Event Form as adverse events unless they increase in severity during the study.

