8.2 Definition

8.2.1 Baseline

The baseline values are those that are obtained at the closest visit prior to the surgery. The arithmetic difference between the baseline and a post-baseline (post-operative for this study) are as follows:

Change from baseline = (post-baseline value – baseline value)

Percent change from baseline = Change from baseline ÷ baseline value × 100.

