9.6 Analysis on PRO Data

The total score is calculated for Visual Function Symptom Impact (range from 0 to 55) and for Local Eye Symptom Impact (range from 0 to 35) will be calculated for each subject at baseline, 3 months, 12 months, and 24 months. The change in these total scores from baseline to the postoperative visits will be derived for each subject.

Descriptive statistics for the continuous variables will be used to summarize these total scores at each visit for the two study groups separately. No inferential statistics will be provided since no labeling claims will be made based on the results.

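### SAP 9.5.3 specifies no within-eye comparison with the pre-procedure exam, so examination findings that persist from entry dilute the by-visit safety tables

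*SAP*

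**What the plan says.** SAP 9.5.3 has two parts. For graded or categorical examinations it promises "The number and percent of subjects reported with each kind of slit lamp findings, gonioscopy findings, dilated fundus examination findings", with pachymetry also listed, at each visit and separately by arm. For continuous measures, "The descriptive statistics for the continuous variables will be derived for the visual field mean deviation (MD) and pattern standard deviation (PSD), and pachymetry". Neither part mentions the same eye's pre-procedure value, a shift table, or a definition of a new or worsened finding.

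Other parts of the plan do refer to baseline:

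- SAP 9.5.2 tabulates acuity at each visit and then adds lines gained and lost, down to "decrease 2 lines, and decrease ≥ 2 lines at each postoperative visit will be calculated for the two study groups separately".
- SAP 9.6 says of the questionnaire: "The change in these total scores from baseline to the postoperative visits will be derived for each subject".
- Protocol 10.0 sets the adverse event rule: "Conditions which exist at the time the subject is enrolled do not need to be recorded" as adverse events unless they increase in severity.
- SAP 8.2.1 defines baseline as the value from the closest visit before surgery and defines change from it. SAP 9.5.3 does not invoke that definition, and SAP 8.1 promises confidence intervals for change only for endpoints it does not name.

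Protocol 6.2 and SAP 4.2 list slit lamp, gonioscopy, fundus and pachymetry results as safety endpoints or outcomes. Visual field is in neither list; as a safety summary it enters only through SAP 9.5.3.

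**The concern.** The by-visit percentage mixes two groups: eyes that had the finding before the procedure and still have it, and eyes that acquired it afterwards. Only the second group bears on the safety of the procedure.

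The first group need not be empty in this trial. Protocol 7.2 excludes capsule opacification only when it is moderate or severe. One route to diagnosis in Protocol 7.1 consists of disc and nerve fibre layer abnormalities. The visual field route requires an MD between -3 and -12 dB.

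SAP 9.5.3 also does not say whether grade enters the count. Iris and corneal findings are graded from 0 to +3 in Appendix 1 of the protocol, yet as the SAP is worded an eye that goes from mild to severe need not change the tabulated number.

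What is at stake is how clearly these tables can show an excess of new findings in one arm. The effectiveness conclusion is not affected.

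**Working it through.** **Numbers per arm.** The plan gives no figure for these tables. The illustration uses 149 randomized per arm, which follows from the SAP's 134 at 12 months and 10% dropout: 134 / 0.9 = 148.9, rounded up to 149.

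**Assumptions, none from the documents.** A share b of eyes has the finding at baseline in both arms, and all of these findings persist. New onset among the remaining eyes is 10% with VISCO360 and 3% with SLT. All 149 eyes per arm are in the denominator.

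**Formulas.**
- Raw prevalence at a visit: p = b + (1 - b) x incidence.
- Share with a new finding: q = (1 - b) x incidence.
- 95% CI half-width of the difference: 1.96 x sqrt{[p1(1 - p1) + p2(1 - p2)] / 149}, and the same with q.

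**At b = 40%.**
- Raw: 0.40 + 0.60 x 0.10 = 46.0% v 0.40 + 0.60 x 0.03 = 41.8%. Half-width 1.96 x sqrt[(0.2484 + 0.2433)/149] = 11.3 points.
- New: 6.0% v 1.8%. Half-width 1.96 x sqrt[(0.0564 + 0.0177)/149] = 4.4 points.

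| Baseline prevalence | Raw, VISCO360 v SLT | Half-width | New, VISCO360 v SLT | Half-width | Difference |
|---|---|---|---|---|---|
| 40% | 46.0% v 41.8% | 11.3 | 6.0% v 1.8% | 4.4 | 4.2 |
| 20% | 28.0% v 22.4% | 9.8 | 8.0% v 2.4% | 5.0 | 5.6 |
| 0% | 10.0% v 3.0% | 5.5 | 10.0% v 3.0% | 5.5 | 7.0 |

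The expected absolute difference is the same on either count. The raw count has a wider interval and a ratio nearer to 1: at 40%, 46.0/41.8 = 1.1 against 6.0/1.8 = 3.3.

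**Sensitivity to the assumed rates.** With new onset 10% v 2% and 134 per arm, the ratio of new findings is 5 throughout. In raw prevalence it appears as:

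| Baseline prevalence | Raw ratio | Half-width, raw | Half-width, new |
|---|---|---|---|
| 10% | 1.6 | 8.6 | 5.3 |
| 20% | 1.3 | 10.3 | 5.1 |
| 30% | 1.2 | 11.3 | 4.8 |
| 50% | 1.1 | 11.9 | 4.1 |

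**Continuous measures.** With equal variances at the two visits and baseline-to-visit correlation r, SD of change / SD of raw value = sqrt[2(1 - r)]. This is 1.00, 0.77, 0.63, 0.45 and 0.32 at r = 0.5, 0.7, 0.8, 0.9 and 0.95. Change is the more precise summary only when r exceeds 0.5. The documents give no correlation for MD, PSD or pachymetry.

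**The case against.** The strongest reply is that new harm is already captured elsewhere. Protocol 10.0 keeps pre-existing conditions out of the adverse event record unless they worsen. Protocol 6.2 makes the comparison of all adverse events through 12 months the primary safety analysis, with a 95% CI around the difference in rate, and SAP 9.5.1 adds severity and relationship to the procedure. This stands as real but partial cover, because it depends on a graded change being recorded as an adverse event. The list of anticipated events is not in the available text, so the overlap cannot be checked either way.

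Further points that stand:

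- SAP 9.5.3 plans descriptive tables without a between-arm interval. The half-widths above therefore measure how informative the tables can be and do not describe a planned test.
- For continuous measures the SAP is silent on change; it does not rule it out.
- Several relevant findings should be rare at entry. Protocol 7.2 excludes abnormal angle anatomy, including synechiae and rubeosis. For these the two counts agree.

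The wording on each visit probably includes the preoperative one, since SAP 9.5.2 separates each visit from each postoperative visit. A baseline column would help. But two group percentages cannot show which eyes kept a finding, lost it or gained it, so this does not close the gap.

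A reader might infer that the tables would be biased against one arm. The documents do not support that: randomization balances entry findings in expectation. Nor does the SAP call a finding seen at a visit new or procedure-related. A reader might also take visual field to be a named safety endpoint, or work out a gain in dB from the -3 to -12 dB range. Visual field is not in Protocol 6.2 or SAP 4.2, and that range binds only one of two and/or routes to diagnosis, so it does not fix the spread of MD among enrolled eyes.

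**Conclusion.** The gap is real and minor. SAP 9.5.3 specifies no within-eye comparison, so for any finding that is common and persistent at entry the planned tables give a diluted view of new findings. Under the assumed rates of 10% v 3% new onset, the interval on raw prevalence is about 2.6 times as wide as on new findings at 40% baseline prevalence (11.3/4.4), about twice as wide at 20% (9.8/5.0), and the same at 0%. The size rests on assumed prevalence, onset and persistence. For MD, PSD and pachymetry the benefit of change requires a correlation above 0.5.

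This does not mean that new harm goes unreported, since the adverse event analysis carries part of that load.

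**What to change.** Keep the by-visit tables in SAP 9.5.3 and add, by arm:

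- for slit lamp, gonioscopy and fundus findings, baseline-to-visit shift tables, or counts of eyes whose finding is new or at least one grade worse than at the same eye's last pre-procedure exam, with the denominator stated;
- for MD, PSD and pachymetry, change from baseline as defined in SAP 8.2.1.

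Between-arm 95% CIs are optional. If given, label them descriptive, because there would be many and none is adjusted for multiplicity. Raw values need not move to listings.

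The protocol already calls for screening gonioscopy, visual field and pachymetry, and capsule opacification is graded for eligibility. The visit schedule table and the fundus grading section cannot be read in the available text, so confirm which pre-procedure fundus exam and scale apply. The cost is SAP wording and programming, with a few more tables. SAP 1.0 allows such an amendment before database lock.

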9.6 Analysis on PRO Data

The total score is calculated for Visual Function Symptom Impact (range from 0 to 55) and for Local Eye Symptom Impact (range from 0 to 35) will be calculated for each subject at baseline, 3 months, 12 months, and 24 months. The change in these total scores from baseline to the postoperative visits will be derived for each subject.

Descriptive statistics for the continuous variables will be used to summarize these total scores at each visit for the two study groups separately. No inferential statistics will be provided since no labeling claims will be made based on the results.
